6 CLINICAL INVESTIGATION PLAN

6.1 Overall Study Design

This will be a phase III, multicentre, prospective, randomised, open-label, two-parallel groups study, followed by a follow-up period.

[figure not shown]
The study plan included a 6-week treatment period, from visit V1 to visit V4, of first-diagnosis patients presenting upper symptoms related to diagnosis of GERD, in the presence/absence of typical symptoms. Patients will be randomised to receive an open-label treatment (in a 1:1 ratio) with Gerdoff®- omeprazole (PPI) (Group 1) or omeprazole (PPI) alone (Group 2). The first administration of investigational products started in the morning of the day following visit V1.

At visit V4, patients in Group 2 who will be treated with omeprazole (PPI) alone, and patients in Group 1 who will be treated with Gerdoff®- omeprazole (PPI) and will be classified as non-responder, completed the study and the most appropriate therapy to treat their symptoms will be prescribed by the investigator.

To assess the maintenance of the effects of treatment, at visit V4 (end of study visit), patients in Group 1 who will be treated with Gerdoff®- omeprazole (PPI) and will be classified as responders could continue with a 12-week follow-up period. During the follow-up period patients could be randomly assigned as open-label (in a 1:1 ratio) to treatment with Gerdoff® or to a control group, which will not receive any treatment. To safeguard the health and well-being of patients, and to keep under control the possible upper symptoms of GERD that could appear, all patients that continued in the follow-up period received omeprazole as rescue medication in a quantity adequate to cover the entire follow-up period. This therapy will be chosen by the study coordinator as it is the treatment commonly used in clinical practice for the treatment of all specific and non-specific symptoms of GERD. The investigator explained to patients that rescue omeprazole could be taken only if necessary and according to the indications given by the Investigator, at constant dosage, and that use will be to be recorded in the daily diary by indicating the reason for administration. The investigator had to report the data in the source documents and in the electronic case report forms (eCRF).

A schematic diagram of the study design follows (Figure 1):

Figure 1. Study diagram

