6.5.3 Study Endpoints

Primary performance variable

The primary performance variable of the study will be the change from baseline to visit V4 of the total score of RSI questionnaire, used to assess the effect of treatment on upper symptoms. The RSI questionnaire examines 9 items, to be scored from 0 to 5, with a higher score indication a higher severity of the symptom (range of total score: 0-45).

Secondary performance variables

The secondary performance variables of the study will be:

- Change of the total score of RSI questionnaire from baseline to the other time points;
- Change of the score of single items of the RSI questionnaire from baseline at any time point;
- Number and percentage of responder/non-responder patients at end of treatment (visit V4);
- Change from baseline to end of treatment (visit V4) and end of follow-up (visit V6) of upper symptoms, assessed using the Likert scale. The Likert scale scored symptoms from 0 to 4, with a higher score indication a higher frequency of the symptom;
- Presence of upper symptoms at baseline, end of treatment (visit V4) and end of follow-up (visit V6), assessed using the RSI questionnaire and the Likert scale:
- Use of rescue medication during the follow-up period: administered therapy, frequency of administration, timing of administration and administered dose;
- Patient's opinion of satisfaction with treatment, requested at intermediate Visits V2 and V3, and at the end of treatment visit V4, by means of a semiquantitative ordinal scale, where: 0 = low, 1 = discrete, 2 = good, 3 = excellent.

Safety variables

The safety variables of the study will be:

- Frequency of adverse events and incidents occurring at any time, during the study;
- Changes from baseline of haematology and blood chemistry parameters;
- Changes from baseline of vital signs (weight, BMI, blood pressure, heart rate and respiratory rate).

Incidents and adverse events

Incidents

According to MEDDEV 2.12.1, Rev. 8, a medical device incident is defined as 'any malfunction or deterioration in the characteristics and/or clinical performance of a device, as well as any inadequacy in the labelling or the instructions for use, which, directly or indirectly, might lead to or might have

led to the death of a patient, or a user or of other persons or to a serious deterioration in their state of health'.

A medical device incident that required reporting included:

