8.1 Sample Size Justification

Although a search in literature has not identified any published article for trials that used the same investigation design as that used in the present study, some recently published articles (9, 13-15) allowed to formulate a sample size calculation for the present investigation.

The calculation of the sample size will be based on the primary objective of the investigation, i.e. to assess the change of RSI questionnaire from baseline to 6 weeks of treatment in the two treatment arms, Gerdoff®- PPI and PPI alone, based on an hypothesis that the addition of Gerdoff® to PPI could improve the effect of disappearance and of rapidity of control of upper symptoms of GERD. Such effect will be evaluated as the mean change in RSI compared to baseline, taking into consideration the variable age, standard deviation (SD) and expected value after treatment with omeprazole.

The following assumptions will be made for the sample size calculation:

Difference between the two arms (delta): 3.6; SD of the difference: 5.

Based on these assumptions, for a comparison based on unpaired Student t test, at a power of 80% and a level of probability of 5% for a two-tailed test, 62 patients (31 in each treatment arm) will be to be included in the study. Estimating a drop-out rate of 20%, 78 patients (39 in each treatment arm) will be to be included in the study.

The software PS Power and Sample Size Calculations Version 3.0, January 2009, will be used for the sample size calculation.

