8.3.1 Primary Performance Analysis

In the analysis of primary performance variable, i.e. the mean difference from the baseline (delta) of the RSI score measured after 6 weeks of treatment, the two treatment groups will be compared using a Student's t-test for independent data.

The test results will be tabulated with the appropriate descriptive statistics and with the calculation of the 95% CI of the difference relative to the delta between the two study treatments.

The primary objective of the study will be achieved only if the statistically significant difference between the two study treatments with the current delta value will be coincident with that planned in the calculation of the numerosity, i.e. 3.6.

Sensitivity analyses will be conducted on the primary performance variable. The study of the temporal profile of the RSI questionnaire will be performed using the analysis of variance for repeated measures (ANOVA). In addition to the treatment effect, the time effect and the treatment by time interaction will be included in the model.

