8.3.2 Secondary Performance Analyses

All secondary variables will be listed and presented with the most appropriate descriptive statistics.

Number and percentage of responder/non-responder patients at end of treatment (visit V4)

Patients who at the 6th week of treatment showed a reduction of at least 50% vs. the baseline and an

absolute value < 13 will be considered as responders. The Chi-square test with the correction of Yates or, if more appropriate, the Exact Fisher's test will be used to compare the distribution of the proportions of responders and non-responders in the two treatment groups. The patients responders in the group treated with Gerdoff® + PPI entered the follow-up period and continued in the observation according to the procedures provided by the study protocol;

Change of frequency of symptoms from baseline to end of treatment (visit V4) of frequency of symptoms, assessed using the Likert scale

The same analyses foreseen for the RSI questionnaire will be performed.

Use of rescue medication

In the first 6 weeks of treatment, the intake in each treatment group of the rescue medication, allowed or not allowed, will be calculated as the frequency of intake of the specific drug and the comparison between groups will be performed using the Fisher's exact test.

In the first 6 weeks of treatment, the comparison of the median dose of rescue medication in the two study groups will be performed by means of the non-parametric (distribution-free) test of the median. If a mean value of intake could also be calculated, the comparison between the two treatment groups will be performed using the Mann-Whitney U test.

Patient satisfaction of treatment

This evaluation will be expressed with a semi-quantitative ordinal scale: 0 = low, 1 = discrete, 2 = good, 3 = excellent). The frequencies of judgments will be compared between groups using the Chisquare Mantel-Haenszel test.

In the follow-up period, the efficacy data collected will be presented by treatment group using only the most appropriate descriptive statistics and consistent with the current numerosity of the sample.

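### The repeated-measures ANOVA in section 8.3.1 has no term that tests the week-6 RSI change, so it should not serve as a sensitivity analysis of the primary result unless a V4 contrast is named

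*Combined protocol and SAP*

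**What the plan says.** Section 6.5.3 fixes the primary variable: "The primary performance variable of the study will be the change from baseline to visit V4 of the total score of RSI questionnaire". Section 8.3.1 tests it with an unpaired t-test and a 95% CI, and section 8.1 sizes the trial on that test: "Difference between the two arms (delta): 3.6; SD of the difference: 5".

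The last paragraph of 8.3.1 opens with "Sensitivity analyses will be conducted on the primary performance variable". It then says that the temporal profile of the RSI will be studied by repeated-measures ANOVA, and adds: "In addition to the treatment effect, the time effect and the treatment by time interaction will be included in the model". It does not say whether this ANOVA is one of the sensitivity analyses just announced, whether V1 is a level of time, what covariance structure is assumed, or whether an arm difference at V4 will be extracted.

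Two other places matter. Section 8.2 describes sensitivity analyses defined by which patients are included. Section 8.3.2 carries the approach over to the Likert scale: "The same analyses foreseen for the RSI questionnaire will be performed". Section 8.3 sets a two-sided 0.05 threshold unless otherwise specified, and nothing exempts the ANOVA terms.

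**The concern.** A sensitivity analysis should ask the primary question again under different assumptions. The primary question is the arm difference in change at one visit, V4. The ANOVA's treatment term asks whether the arms differ on average over the visits. If V1 is one of them, the average includes a visit where randomisation makes the expected difference zero. The interaction asks whether the two profiles differ in shape anywhere. Neither is the V4 change, even with complete data.

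At stake is how two extra p-values are used. The ANOVA is the only alternative model offered under the primary variable, and it stands directly after the sensitivity sentence. A report could therefore quote either term as confirming the primary result. In an open-label trial with a patient-completed score, a difference at week 1 that fades by week 6 is plausible. It would produce apparent support for a benefit that the primary hypothesis does not show.

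**Working it through.** **Inputs from the documents.** Delta 3.6, SD 5 (read as the SD of the change), two-sided 5%, 80% power, 31 per arm (section 8.1); RSI at V1 to V4, weeks 0, 1, 3 and 6 (section 6.5.1).

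**Assumptions not in the documents.** Complete data; compound symmetry with visit correlation ρ of 0.3, 0.5 or 0.7; the shape of the arm difference over visits.

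**Plan's own figure.** n per arm = 2 × (1.960 + 0.842)² × 5² / 3.6² = 30.3, so 31 per arm and 62 in all. 62 / (1 − 0.20) = 77.5, so 78. Both reproduce. Exact t-test power at 31 per arm is 0.796.

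**Formulas.** Write d₁ to d₄ for the arm differences at V1 to V4 and d̄ for their mean.
- Score variance: σ² = 25 / [2(1 − ρ)], so that the V4 − V1 change has SD 5. Then σ = 4.23, 5.00, 6.45 for ρ = 0.3, 0.5, 0.7.
- Treatment term (V1 a level of time): noncentrality d̄ / [SD × √(2/31)], 60 df, where SD = σ√[(1 + 3ρ)/4] = 2.91, 3.95, 5.68.
- Interaction: λ = (31/2) × Σ(dⱼ − d̄)² / [σ²(1 − ρ)], on 3 and 180 df. The denominator is 12.5 for every ρ.

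**No V4 effect, early difference only.** For 0/3.6/1.8/0, d̄ = 5.4/4 = 1.35, Σ = 8.91 and λ = 15.5 × 8.91 / 12.5 = 11.05. For 0/1.8/0.9/0, d̄ = 0.675, Σ = 2.23 and λ = 2.76.

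| Arm difference V1–V4 | t-test at V4 | Treatment term, ρ = 0.3 / 0.5 / 0.7 | Interaction |
|---|---|---|---|
| 0/3.6/1.8/0 | 0.05 | 0.44 / 0.26 / 0.15 | 0.80 |
| 0/1.8/0.9/0 | 0.05 | 0.15 / 0.10 / 0.07 | 0.25 |

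Simulation agrees within a few points (treatment term 14–42% in the first row). At least one term is significant in about 82–89% of trials in the first row. If changes at V2 to V4 are modelled instead, without V1, the treatment term averages 3.6, 1.8 and 0, which is 1.8. Its SD is √[(25 + 2 × 12.5)/3] = 4.08, and it rejects in about 40% of trials. Leaving V1 out does not cure the mismatch.

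**True V4 effect of 3.6.**

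| Arm difference V1–V4 | t-test at V4 | Treatment term, ρ = 0.3 / 0.5 / 0.7 | Interaction |
|---|---|---|---|
| 0/0.6/1.8/3.6 | 0.80 | 0.51 / 0.31 / 0.18 | 0.72 |
| 0/1.2/2.4/3.6 | 0.80 | 0.67 / 0.42 / 0.23 | 0.70 |
| 0/2.4/3.0/3.6 | 0.80 | 0.85 / 0.60 / 0.33 | 0.72 |

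In simulation over these nine cases, at least one term is significant in about 76–96% of trials. A significant t-test with both terms non-significant occurs in about 2–10%. The pair has two chances to reject, about 10% when there is no effect at any visit, so this is not a like-for-like power comparison. It does show that the ANOVA as a whole would seldom contradict a true primary result.

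**V4 contrast.** With complete data and visit-specific variances, the unadjusted V4-versus-baseline contrast is the t-test: power 0.796, and 5% rejection when the V4 difference is zero, whatever happens at V2 and V3. Adjusting for baseline RSI lowers the residual SD from 5 to σ√(1 − ρ²) = 4.03, 4.33, 4.61. Power is then about 0.93, 0.90, 0.86 (0.84–0.93 by simulation), still with about 5% rejection when the V4 difference is zero.

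**The case against.** The strongest reply is that the ANOVA was never meant to test V4. Section 8.3.1 gives it a purpose of its own, the temporal profile. Section 6.5.3 lists RSI change at the other time points as a secondary variable, and section 8.1 includes speed of symptom control in the hypothesis. On that reading the sensitivity analyses are the population-based ones in section 8.2, and a significant ANOVA under a transient difference is a correct finding about the profile. No text makes the ANOVA part of the success rule. This stands as a defence of the ANOVA itself. It does not remove the ambiguity, because the profile sentence follows the sensitivity sentence directly and no V4 contrast is named.

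A reader might also infer that the ANOVA will miss a true week-6 effect, with a power loss of 20 to 50 points. The documents and the arithmetic do not support that. The loss belongs to the treatment term alone and depends on the assumed correlation. At ρ = 0.3 with a fairly fast onset that term has 0.85 power against 0.80 for the t-test. The interaction keeps about 0.70, and the two terms together lose little or nothing.

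The transient scenario is also demanding, since it puts the whole planned delta at week 1 and nothing at week 6. Halving it brings the treatment term down to 7–15%.

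**Conclusion.** The point holds as a mismatch between the announced sensitivity analysis and what the ANOVA terms test. The risk is false support. Under an early difference gone by V4, the interaction is significant in about 80% of trials and the treatment term in about 15–44%, falling to 25% and 7–15% if the early difference is half as large. The t-test stays at 5%. The treatment term alone is weak for gradual effects (about 18–67% for the two slower profiles), but that does not extend to the ANOVA as a whole.

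The primary test, its confidence interval, its alpha and the sample size are unaffected. The sizes rest on assumed correlations, effect profiles and complete data; the mismatch itself rests on none of these. It is worth correcting but does not threaten the trial's main conclusion.

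**What to change.** In section 8.3.1, and for the Likert scale through 8.3.2:

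- Keep the repeated-measures ANOVA as a descriptive analysis of the profile, and say that its overall treatment and interaction terms will not be quoted for or against the primary result.
- For the model-based sensitivity analysis, model change from baseline at V2, V3 and V4 with arm, visit, arm by visit and baseline score (RSI, or Likert for that scale), allowing visits to be correlated within patient.
- Name the arm difference at V4, with its 95% CI, as the only contrast from this model that bears on the primary result. If speed of onset is of interest, report the V2 and V3 contrasts separately as secondary.
- Leave the population-based sensitivity analyses of section 8.2 as planned.

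The cost is a few sentences and one contrast from data already collected, with no new patients or visits. The downside is that the overall treatment and interaction p-values can no longer be quoted as efficacy evidence.

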8.3.2 Secondary Performance Analyses

All secondary variables will be listed and presented with the most appropriate descriptive statistics.

Number and percentage of responder/non-responder patients at end of treatment (visit V4)

Patients who at the 6th week of treatment showed a reduction of at least 50% vs. the baseline and an

absolute value < 13 will be considered as responders. The Chi-square test with the correction of Yates or, if more appropriate, the Exact Fisher's test will be used to compare the distribution of the proportions of responders and non-responders in the two treatment groups. The patients responders in the group treated with Gerdoff® + PPI entered the follow-up period and continued in the observation according to the procedures provided by the study protocol;

Change of frequency of symptoms from baseline to end of treatment (visit V4) of frequency of symptoms, assessed using the Likert scale

The same analyses foreseen for the RSI questionnaire will be performed.

Use of rescue medication

In the first 6 weeks of treatment, the intake in each treatment group of the rescue medication, allowed or not allowed, will be calculated as the frequency of intake of the specific drug and the comparison between groups will be performed using the Fisher's exact test.

In the first 6 weeks of treatment, the comparison of the median dose of rescue medication in the two study groups will be performed by means of the non-parametric (distribution-free) test of the median. If a mean value of intake could also be calculated, the comparison between the two treatment groups will be performed using the Mann-Whitney U test.

Patient satisfaction of treatment

This evaluation will be expressed with a semi-quantitative ordinal scale: 0 = low, 1 = discrete, 2 = good, 3 = excellent). The frequencies of judgments will be compared between groups using the Chisquare Mantel-Haenszel test.

In the follow-up period, the efficacy data collected will be presented by treatment group using only the most appropriate descriptive statistics and consistent with the current numerosity of the sample.

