- During the first 6-week treatment period, the use of any type of rescue medication will be not permitted, as well as the use of any other therapy for GERD, irrespective of dosage and frequency of administration. In case of intake of any type of rescue medication, patients will be to be considered as protocol violators;
- During the follow-up period only the use of omeprazole will be permitted as rescue medication at constant dose, to be taken only if necessary and according to the indications of the Investigator. The administration of any other therapy for GERD will be not permitted.

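### The weeks 0–6 rescue analysis rests on a median-dose test that is very probably uninformative, gives Fisher's test no unit, and makes the more useful Mann-Whitney test conditional

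*Combined protocol and SAP*

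**What the plan says.** Section 2.2 lists rescue use as a secondary objective for both the first six weeks and the follow-up. For the first six weeks, section 6.4.6 states that "the use of any type of rescue medication will be not permitted", and adds: "In case of intake of any type of rescue medication, patients will be to be considered as protocol violators".

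Section 8.3.2 plans three between-arm analyses for those weeks:

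- Rescue intake, allowed or not, is to be "calculated as the frequency of intake of the specific drug and the comparison between groups will be performed using" Fisher's exact test.
- For dose, "the comparison of the median dose of rescue medication in the two study groups will be performed by means of the non-parametric" median test.
- A Mann-Whitney U test follows, but only if an average intake can be worked out.

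The text does not say whether non-users enter with dose zero, how values tied at the median are treated, how doses of different products are put on one scale, or whether Fisher's test counts patients or intakes. Section 8.3 says in general that categorical variables are summarised as patient counts.

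**The concern.** A median describes dose only if at least about half the patients take the drug. Where the drug is forbidden and taking it is a violation, most patients should have no intake, so a comparison of medians would usually be zero against zero. The one planned test that could use the amounts is subject to a condition that it does not need, since a rank test requires no mean. The wording of Fisher's test leaves room for an analysis that treats repeated intakes by one patient as independent, or for several small tests where one question was asked.

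What is at stake is whether the weeks 0–6 part of a stated secondary objective gets an interpretable answer. The primary comparison is not affected.

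**Working it through.** **Inputs from section 8.1.** "Difference between the two arms (delta): 3.6; SD of the difference: 5", "at a power of 80% and a level of probability of 5% for a two-tailed test". Normal approximation: n per arm = 2 × [(1.960 + 0.842) × 5 / 3.6]² = 30.3, so 31 per arm and 62 in total. With 20% drop-out, 62 / 0.80 = 77.5, so 78, or 39 per arm. The plan's figures reproduce. The documents give no sample size or expected rate for rescue, so every user rate below is an assumption.

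**1. Are the medians zero?** Count non-users as zero. With 39 patients, an arm's median is zero when at most 19 are users. With X ~ Bin(39, p) in each arm, P(both medians zero) = P(X ≤ 19)². For 31 per arm the cut-off is 15.

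| Users per arm | 39 per arm | 31 per arm |
|---|---|---|
| 20% | >0.999 | >0.999 |
| 30% | 0.9957² = 0.991 | 0.9905² = 0.981 |
| 40% | 0.8979² = 0.81 | 0.8716² = 0.76 |
| 45% | 0.54 | 0.51 |
| 50% | 0.25 | 0.25 |

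The median test itself uses the pooled median. P(pooled median above zero) is P(Bin(78, p) ≥ 39 or 40, depending on the median convention): 0.00007 to 0.00017 at 30% users, and 0.028 to 0.047 at 40%.

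**2. What does the median test do when the pooled median is zero?** Take 4/39 users against 12/39.

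- Ties counted as not above the median: the table is 4, 12 / 35, 27, which is users against non-users. Chi-square = 78 × (4×27 − 12×35)² / (16 × 62 × 39 × 39) = 5.03, p = 0.025; with continuity correction p = 0.0497. Fisher's test on the same table gives p = 0.0475. Both arm medians are zero.
- Ties counted as above, or dropped: the test cannot be computed.
- Dose is ignored. With 8/39 users in each arm, at 1 unit in one arm and 14 in the other, the median test gives p = 1.0.

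**3. Does the unit of Fisher's test matter?** By exact enumeration at 39 per arm, the true size on patients is 0.016 at 10% users in both arms and 0.028 at 20%. On intake-days out of 39 × 42 = 1,638 per arm, with 10–30% users and a geometric number of days per user (4,000 runs per setting), simulated type I error is about 19% at a mean of 2 days and about 48% at a mean of 5. With 1 to 14 days equally likely it is about 50%.

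A variance argument agrees. The inflation is about E(D²)/E(D) − p·E(D), where D is days per user. At p = 0.10 this is 6/2 − 0.2 = 2.8 for mean 2, and 45/5 − 0.5 = 8.5 for mean 5. The normal-theory error rates are P(|Z| > 1.96/√2.8) = 0.24 and P(|Z| > 1.96/√8.5) = 0.50; the discrete Fisher test lies a little below these.

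**4. What does splitting by drug cost?** Exact Fisher power at 39 per arm for 30% v 10% any use is 0.52. If that use were spread evenly over three drugs (an assumption), each test compares 10% with 3.3% and has power 0.07.

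**5. What would patient-level analyses achieve?** Fisher power on any use at 39 per arm is 0.40 for 20% v 5%, 0.52 for 30% v 10% and 0.84 for 40% v 10%. At 31 per arm, 30% v 10% has 0.39. Mann-Whitney on days, with zeros for non-users and 1 to 14 days per user, has simulated power of about 0.60 to 0.62 for 30% v 10%, and size of about 0.05. Part of that gain reflects Fisher's conservatism, because most values are tied at zero.

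**The case against.** The strongest case on the other side is that section 8.3.2 is incomplete rather than unworkable. Three stronger readings are tempting, and the documents support none of them.

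- *The medians will be zero.* No rescue rate is given, and non-users are not said to enter as zero. At 40% users there is about a 19% chance (1 − 0.81) that at least one arm's median exceeds zero. Restricting to users would avoid the zeros, but would no longer compare the randomised groups.
- *The planned tests cannot compare rescue use.* Under one tie rule the median test does compare users with non-users, and Mann-Whitney, if run, is usable. Its condition may mean only that an intake must be calculable for each patient.
- *Fisher's test is set on intakes.* No unit is named, and the general rule in section 8.3 points to patients. The inflated error rates apply to one reading only.

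Nor is rescue the only sign of failed control outside the questionnaires. Diaries record daily symptoms (section 7.4), the specialist assesses symptoms at each visit (section 6.5.2), and early discontinuation counts as treatment failure (section 6.3.3). The endpoint list in section 6.5.3 names rescue only for follow-up. Section 8 also refers to a final SAP in Annex 10; if that is a separate text and settles these details, section 8.3.2 need only be aligned with it.

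These points limit the concern. They do not supply the missing unit, zero rule, tie rule or dose scale, and they do not make a median dose informative for a prohibited drug.

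**Conclusion.** The concern holds as one of specification and choice of test. If non-users count as zero, the median-dose comparison is near certain to be uninformative up to about 30% users (probability 0.991 at 39 per arm) and probably so at 40% (0.81). This rests on assumed user rates, taken as equal in the two arms. Fisher's test needs a stated unit: on patients it is valid and conservative, whereas on intakes its error rate would be several times nominal under the assumed patterns. The Mann-Whitney test should not be conditional. The reach is one secondary objective; the primary analysis and sample size are unaffected.

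**What to change.** Rewrite the weeks 0–6 paragraph of section 8.3.2 with one row per ITT patient:

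1. Any GERD therapy outside the assigned regimen, yes/no. Include a changed omeprazole dosage, which section 8.2 names beside additional therapy and which a rule limited to other products would miss. Use Fisher's exact test, with the risk difference and 95% CI.
2. Number of days with such intake, zero for non-users. Use the Mann-Whitney test without condition. State how early discontinuers are counted, for example as days of intake per day observed, or ranked worst because section 6.3.3 treats them as failures. Otherwise a patient withdrawn after one intake scores as a light user.

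Delete the median test and the per-drug tests, and list drugs and doses descriptively.

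Three inconsistencies should be reconciled at the same time: section 8.3.2 speaks of allowed rescue in weeks 0–6 while section 6.4.6 allows none; section 6.5.3 confines the rescue variable to follow-up while sections 2.2 and 8.3.2 do not; and section 6.3.3 lists other GERD therapy among reasons requiring discontinuation while section 6.4.6 leaves continuation to the investigator.

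The cost is a small wording change, since the diary already records the data. The downsides are that no formal test remains for individual drugs and that power stays modest: about 52% for 30% v 10% at 39 per arm.
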